The detailed sample size calculation for each study outcome is attached in Appendix B. The required sample size is based on the requirements for the development and validation of the least common DM complication of ESRD. Specifically, based on our previous study, the 5-year incidence of ESRD was 1.9%(8), which can be extrapolated to a 10-year incidence of ESRD was 3.8% by assuming a constant incidence rate over time. To develop the risk prediction model for ESRD by multivariable Cox proportional hazard regressions with forward stepwise variables selection on 16 potential risks factors, we need 21,053 subjects using the 1 in 50 rule that 1 candidate predictor can be studied for every 50 events (23). To validate the risk prediction models, the area under the receiver operating characteristic curve (AUC) will be used to assess the discriminatory power of the predictive model on a separate sample of subjects. With 10 years incidence rate of ESRD was 3.8%(8), a total 14,307 subjects (544 subjects with ESRD and 13,763 subjects without ESRD) is needed to

ensure a precision of 0.05 for AUC of 0.7 by a 95% confidence interval.

Hence, a total 35,360 male and 35,360 female are needed for the development (training dataset) and validation of risk prediction models stratified by gender. The HA data set that we have obtained for our 5-year evaluation of quality of care and effectiveness of RAMP-DM study(8) has identified 120,857 DM patients under the care of public primary care on or before 1 Jan 2009, so we should be able to obtain sufficient number of subjects.

(iii) **Methods**

Each patient will be followed from 1 July 2006 to 31 December 2016 for the development of the indicator DM complications and mortality.

Definition of indicator DM complications

The incidence of four major DM complications (CHD, stroke, heart failure and ESRD), total CVD and all-cause mortality will be calculated. The incidence is counted from the earliest date of documented diagnosis defined by the relevant ICPC-2 and/ or ICD-9-CM coding recorded in the HA CMS database from 1 July 2006 to 31 December 2016. The relevant ICPC-2 and ICD-9-CM codes of each DM complication and mortality are determined by the academic and HA clinician co-investigators as listed below:-

1. CHD (ischaemic heart disease, myocardial infarction (MI), coronary death or sudden death) is defined by any of ICPC-2 K74 to K76 and ICD-9-CM 410.x, 411.x to 414.x, 798.x

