3. 10-year risk prediction models for total CVD, all-cause mortality and each of 4 major DM complications
4. Factors that have sufficient power to classify Chinese DM patients in primary care into risk group in terms of total CVD and all-cause mortality.

(iv) **Data processing and analysis**

The cohort will be stratified by gender. Descriptive statistics will be used to calculate the incidence of total CVD, all-cause mortality and each of 4 major DM complications will be analysed annually and cumulatively over 10 years with a 95% confidence interval. The distribution of risk factors will be cross-tabulated by complication or mortality events. The 10 year cumulative incidence of various DM complications and mortalities will be further analysed by Kaplan-Meier method. The Kaplan-Meier survival curve will be used to describe the survivorship of total CVD, all-cause mortality and each of 4 major DM complications in the study cohort over 10 years. Unadjusted associations between the risk factors and odds of events will be assessed by independent t-test for continuous variables or Chi-square test for categorical variables.

The cohort will be randomly split on a 2:1 basis, with the two-third sample used for developing the risk prediction models, and the other one-third sample used for validation of the risk prediction models. The analyses will be carried out separately for men and women.

Development of risk prediction models

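### The stated minimum of 35,360 per sex does not fit the 2:1 split: at that size validation gets 11,787 subjects, not the 14,307 calculated; a 2:1 minimum is 42,921 per sex

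*Combined protocol and SAP*

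**What the plan says.** Section d)(ii), under the sample size heading, sizes the study on ESRD, the rarest complication, with an assumed 10-year incidence of 3.8%. It derives two separate requirements.

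- Development, with 16 candidate predictors: "we need 21,053 subjects using the 1 in 50 rule".
- Validation, on a different set of subjects: "a total 14,307 subjects (544 subjects with ESRD and 13,763 subjects without ESRD) is needed to" reach a target, which the plan gives as 0.05 precision at an AUC of 0.7 with 95% confidence.

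It adds the two and applies the sum to each sex: "a total 35,360 male and 35,360 female are needed for the development (training dataset) and validation of risk prediction models". It then cites 120,857 patients identified in an earlier data set dated 1 January 2009 and concludes, "so we should be able to obtain sufficient number of subjects".

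Section d)(iv) sets the division of the cohort: "The cohort will be randomly split on a 2:1 basis", with two thirds for development and "the other one-third sample used for validation of the risk prediction models". It adds: "The analyses will be carried out separately for men and women".

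Section f) (Existing Facilities) makes a second feasibility claim. It refers to a cohort of 90,000 primary care patients and expresses confidence that the required number can be found in it.

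**The concern.** Adding the two requirements gives a sufficient total only if the cohort is divided in the proportion of those requirements, 21,053:14,307, or about 1.47:1. A 2:1 split moves subjects from validation to development, so a cohort of exactly the stated size over-supplies development and under-supplies validation. Nothing in the supplied text reconciles the two sections.

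Two things are at stake. First, the stated minimum does not secure the precision of the validation AUC that it was calculated to secure. Second, the feasibility conclusion is judged against a total that is too small for the split the plan will use.

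**Working it through.** **Inputs.** From d)(ii): 10-year ESRD incidence 3.8%, 16 candidate predictors, 50 events per predictor, AUC 0.70, precision 0.05 at 95% confidence, 14,307 for validation (544 with ESRD, 13,763 without), and a pool of 120,857. From d)(iv): a 2:1 split and separate analyses by sex. From f): a cohort of 90,000.

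**1. Reproduce the plan's figures.**

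- Development: 16 × 50 / 0.038 = 21,052.6, rounded up to 21,053. Exact.
- Validation: the variance formula is not named in the supplied text, and Appendix B, which holds the detail, was not available. I used the Hanley-McNeil variance with Q₁ = A/(2 − A) = 0.5385 and Q₂ = 2A²/(1 + A) = 0.5765 at A = 0.70:

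  SE² = [A(1 − A) + (n₁ − 1)(Q₁ − A²) + (n₀ − 1)(Q₂ − A²)] / (n₁n₀)

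  With n₁ = 544 and n₀ = 13,763, SE = √[(0.21 + 26.31 + 1,190.01) / 7,487,072] = 0.01275. The half-width is 1.96 × 0.01275 = 0.0250 and the full width is 0.0500.
- Solving for a full width of 0.05 gives 14,297, against 14,307 stated. Solving for a half-width of 0.05 gives 3,575. Full width is therefore the reading that best reproduces the plan.
- Sum: 21,053 + 14,307 = 35,360. Exact, and 21,053 / 35,360 = 59.5%.

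**2. Apply the 2:1 split to 35,360 per sex.**

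| | Needed | Obtained at 2:1 | Difference |
|---|---|---|---|
| Development | 21,053 | 23,573 | +2,520 |
| Validation | 14,307 | 11,787 | −2,520 (−17.6%) |

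Expected validation events: 11,787 × 0.038 = 448, against 544.

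Precision with 448 and 11,339: SE = √[(0.21 + 21.66 + 980.40) / 5,079,872] = 0.01405. The full width is 2 × 1.96 × 0.01405 = 0.055 (half-width 0.0275).

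**3. Minimum under 2:1.**

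N must satisfy N/3 ≥ 14,307 and 2N/3 ≥ 21,053:

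N = max(3 × 14,307; 1.5 × 21,053) = max(42,921; 31,580) = 42,921 per sex, made up of 28,614 for development and 14,307 for validation.

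Both sexes: 2 × 42,921 = 85,842, against 2 × 35,360 = 70,720. The difference is 15,122 (21.4%).

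**4. Feasibility against the pools cited.**

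| Pool | Share needed for 70,720 | Share needed for 85,842 |
|---|---|---|
| 120,857 | 58.5% | 71.0% |
| 90,000 | 78.6% | 95.4% |

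These shares assume an even sex split, which the documents do not give, and apply before the 2006 eligibility criteria. With an uneven split the smaller sex governs: the eligible fraction times its share of the 120,857 must reach 42,921 / 120,857 = 0.355, instead of 0.293. At an assumed 45:55 split that means 0.355 / 0.45 = 79% eligible.

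If all 120,857 were eligible and evenly split by sex, validation would have 120,857 / 6 = 20,143 per sex, with a full width of about 0.042. From 90,000 on the same terms it would have 15,000, still above 14,307.

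**The case against.** The strongest reply is that 35,360 is a floor and not a target. The plan takes every eligible patient, so validation gets 11,787 only if the cohort happens to be exactly that size. The pool of 120,857 also exceeds the corrected total of 85,842. This stands, and it is why the point is minor. It does not settle feasibility: the pool is dated 1 January 2009, the cohort must qualify by 1 July 2006 and be free of complications, and the documents do not say how many of the 120,857 meet those conditions. The 90,000 in section f) leaves less room.

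The loss of precision is also slight and may be confined to ESRD. An outcome with an incidence of about 4.6% or more would meet the 0.050 width with 11,787 subjects, and ESRD was chosen as the rarest complication. By the same token, the shortfall is small beside the uncertainty in an extrapolated 3.8%. This also stands.

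Finally, the 0.055 is inferred, because the plan does not say whether precision means full or half width. If it meant half-width, about 3,575 would suffice, but that does not reproduce 14,307. The mismatch of 11,787 against the plan's own 14,307 needs no view on this.

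**Conclusion.** The concern holds, as a minor internal inconsistency. Both component figures reproduce; the error lies in adding them while dividing the cohort 2:1. At the stated minimum, validation falls 2,520 subjects per sex short of the plan's requirement, and the 2:1 minimum is 42,921 per sex. These results use only the plan's own numbers. The widening of the full ESRD AUC interval from 0.050 to about 0.055 rests in addition on the Hanley-McNeil variance, the full-width reading and the 3.8% incidence. The planned analysis is not invalidated, and the cohort may well be large enough; what is wrong is the stated minimum and the feasibility argument built on it.

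**What to change.** Choose one of the following.

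1. **Preferred.** Keep 2:1, restate the minimum as 42,921 per sex (85,842 in total), and restate the feasibility sentence in d)(ii) against that total. Check the feasibility claim in f) against the same number.
2. Keep 35,360 and 2:1, and state that at this minimum the full 95% interval for the ESRD AUC is about 0.055 wide.
3. Keep 35,360 and divide the cohort exactly 21,053:14,307. A rounded 60:40 split would give validation 0.4 × 35,360 = 14,144, still 163 short.

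In every case, say whether the precision of 0.05 is a full width or a half-width.

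Options 1 and 2 cost only corrected text; data extraction and analysis do not change, because all eligible records are used. Option 3 also changes the split in d)(iv).

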1. Calculate the 10 years incidence of total CVD, all-cause mortality and each major DM complication in Chinese DM patients in primary care.
2. Determine the risk factors that significantly predict total CVD, all-cause mortality and each major DM complication for Chinese DM patients in primary care.
3. Develop and validate risk prediction models for total CVD, all-cause mortality and each major DM complication for Chinese DM patients in primary care.
4. Develop a risk prediction nomogram and chart for the risk of total CVD, all-cause mortality for Chinese DM patients in primary care

Hypotheses

The following hypotheses will be tested:

1. Patient socio-demographic, clinical parameters, disease characteristics, and treatment modalities (these independent variables are described in the Methods section) are predictive of 10-year risk of total CVD, all-cause mortality and individual DM complication as a dependent variable.
2. The risk prediction models for total CVD, all-cause mortality and individual DM complication developed in this study can have over 70% of discriminating power.

d) **Plan of Investigation:**

(i) **Study design**

A 10-year retrospective study on a population-based cohort of Chinese DM patients in primary care.

(ii) **Subjects**

The cohort will include all patients with a documented clinical diagnosis of DM and were receiving care in the Hospital Authority (HA) primary care General Out-Patient Clinics (GOPC) and Family Medicine Clinics (FMC) on or before 1 July 2006 identified from the HA clinical management system (CMS) database.

Inclusion criteria

1. Age \geq 18 years old
2. At least 1 GOPC/FMC attendance on or within 1 year before 1 July 2006
3. Had a CMS record of the coding of ICPC-2 of T89 (Diabetes insulin dependent) or T90 (Diabetes non-insulin dependent) on or before 1 July 2006

Exclusion criteria

1. Patients who had a diagnosis of any DM complications defined by the relevant ICPC-2 or ICD-9-CM (shown in the Method section) on or before 1 July 2006.
2. Patients exclusively managed by Specialist Out-Patient Clinic (SOPC) on or before 1 July 2006.

Sample size calculation

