2. Stoke (fatal and non-fatal stroke) is defined by any of ICPC-2 K89 to K91 or ICD-9-CM 430.x to 438.x.
3. Heart failure is defined by any of ICPC-2 K77 or ICD-9-CM 428.x
4. CVD is defined as the presence of any of CHD, heart failure and stroke ICPC-2 or ICD-9-CM codes listed in 1, 2 and 3 above.
5. ESRD is defined by any of ICD-9-CM 250.3x, 585.x, 586.x, or an eGFR<15mL/min/1.73m².
6. Mortality is identified from the Hong Kong Death Registry.

Risk factors to be Included in the Risk Prediction Models

Risk factors (independent variables) previously found to be associated with DM

complications from the literature (4) and those that are routinely available in primary care are selected to strike a balance between comprehensiveness and feasibility. The potential risk factors that will be explored include those related to patient's socio-demographics, clinical parameters, disease characteristics and treatment modalities. Patient socio-demographics include sex, age and smoking status. Clinical parameters include body mass index (BMI), haemoglobin A1c (HbA1c), systolic and diastolic blood pressure, lipid profile (total cholesterol, HDL-C, LDL-C, triglyceride), estimated glomerular filtration rate (eGFR) and albuminuria. Disease characteristics include the duration of DM and co-morbidity. Treatment modalities include the use of specific anti-hypertensive drugs, insulin, specific oral anti-diabetic drugs and lipid-lowering agents. The operational definitions of the risk factors are shown in appendix A. These factors, except sex, age, duration of DM and co-morbidity, are modifiable, which have implications for practice.

Data collection

In the middle of 2017, anonymous data from 1 January 2006 to 31 December 2016 of all DM patients who satisfy the inclusion criteria and without any exclusion criteria will be extracted by the HA statistics team from the HA clinical management system (CMS) database. We have successful experience in working with the HA in the extraction of similar data from 2009 to 2013 for our extended evaluation on quality of care and effectiveness of RAMP-DM study (7), and we have obtained preliminary agreement from the HA for the data extraction in the present study.

Outcome Measures

1. The incidence of total CVD, all-cause mortality and each of 4 major DM complications over 10 years
2. Factors predictive of total CVD, all-cause mortality and each of 4 major DM complications over 10 years

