Cox proportional hazard regressions with forward stepwise method will be used to develop the risk prediction models for total CVD, all-cause mortality and each of 4 major DM complications. If the main term of a clinical parameter is selected in the models, the quadratic term of such clinical parameter will be evaluated. Afterwards, the interaction terms between selected predictors and age will be also examined in the risk prediction models. Cox regressions is the most commonly used method in risk prediction models in the Framingham Heart Study (9, 10) and UKPDS (11, 12). It allows us to estimate the risk of disease or death for an individual, given their prognostic variables. A positive hazard ratio means a higher likelihood of event associated with that specific variable. Conversely, a negative hazard ratio means a lower likelihood of the event associated with that specific variable. The key proportional hazards assumption will be assessed by examining plots of the scaled Schoenfeld residuals against time for the covariates. Any non-random pattern indicates a violation of the proportional hazards assumptions in which case transformation of covariates may be considered. For example, all continuous variables were naturally logarithmically transformed to minimize the influence of extreme values and to

improve discrimination and calibration of the models. A parametric approach such as exponential or Weibull distribution for the hazard function can also be carried out. A total of 6 risk prediction models will be established for total CVD, all-cause mortality and each of 4 major DM complications. The log of the hazard ratio of each selected risk factor in the final model will be used as coefficient weights in the prediction model of each relevant outcome. The risk equations for 10 year's follow-up will be established by combining these weights with the survivor function(9). A receiver operating characteristic (ROC) curve of predicted risk against observed events will be used to determine the risk threshold for the predicted outcomes as the risk threshold with the highest sum of sensitivity and specificity of the actual observed events.

Validation of risk prediction models

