To validate the risk prediction models for total CVD, all-cause mortality and each of 4 major DM complications, they will be applied to the data of the one third validation sample to estimate the risk level of the subjects. A receiver operating characteristic (ROC) curve of predicted risk against observed events will be used to calculate the area under the curve (AUC) for assessing overall prediction accuracy. The corresponding 95% confidence interval will be obtained by bootstrapping of size 2000. An AUC of less than 0.7 indicates limited discriminating power, 0.7 to 0.8 is acceptable, and higher than 0.8 suggests strong discrimination of the predictive models. Using the optimal prediction risk threshold identified by ROC curve in training dataset, and the corresponding sensitivity and specificity of the models against observed events will be calculated to further evaluate the performance of the models.

Calibration will be used to measure how closely predicted outcomes agree with actual outcomes. Calibration of the model's ability to correctly estimate the absolute risks will be examined by modified Hosmer-Lemeshow test and calibration plots. The modified Hosmer-Lemeshow test for time to event data measures how well the predicted probability of the expected event rate agrees with the observed event rate, where a *p*-value higher than 0.05 indicates good model calibration. In a calibration plot of the observed incidence of events against the predicted risk shows the scatter along the 45° line of perfect fit between predicted risk and observed incidence of event throughout the entire risk spectrum.

The D statistic, R^2 statistic and Brier score will be calculated for assessing the predictive power of the model. The D statistic is a measure of discrimination where higher value indicates better discrimination. The R^2 statistic is a measure of explained variation with a higher value indicating better performance. The Brier score is a measure of goodness of fit in which a lower value mean higher accuracy.

Development of a risk prediction nomogram and chart

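### Events are counted over 10.5 years, while incidence, risk equations and validation are labelled 10-year, and no censoring or evaluation at 10 years is stated

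*Combined protocol and SAP*

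**What the plan says.** All patients enter on 1 July 2006 (d)(ii) Subjects). Two statements in d)(iii) Methods fix the window:

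- Follow-up: "Each patient will be followed from 1 July 2006 to 31 December 2016 for the development of the indicator DM complications and mortality".
- Outcome definition: incidence runs from the earliest diagnosis coded in the database, with codes "recorded in the HA CMS database from 1 July 2006 to 31 December 2016".

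The analysis is framed at 10 years:

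- Study design: "A 10-year retrospective study on a population-based cohort of Chinese DM patients in primary care".
- Outcome Measures, item 1: "The incidence of total CVD, all-cause mortality and each of 4 major DM complications over 10 years".
- d)(iv) Data processing and analysis: descriptive incidence "will be analysed annually and cumulatively over 10 years with a 95% confidence interval", followed by a Kaplan-Meier analysis of 10-year cumulative incidence.
- Development of risk prediction models: "The risk equations for 10 year's follow-up will be established by combining these weights with the survivor function(9"). The risk threshold comes from an ROC curve against observed events.
- Validation of risk prediction models: "A receiver operating characteristic (ROC) curve of predicted risk against observed events will be used to calculate the area under the curve (AUC"). Sensitivity and specificity, the calibration plot and the Brier score follow. None of these has a stated evaluation time. The calibration test is a Hosmer-Lemeshow version for time-to-event data, also without a stated time.

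**The concern.** Ten years from 1 July 2006 end on 30 June 2016, so the counting window is half a year longer than the prediction horizon. A patient whose first event falls in October 2016 was event-free at 10 years. If event status follows the outcome definition as written, that patient is a case when a 10-year prediction is scored.

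Two things are at stake. A descriptive 10-year incidence (Objective 1) could include six months of events that do not belong to it. The yes/no and crude-observed validation measures could compare a 10-year prediction with a 10.5-year outcome. The plan reads calibration in absolute terms and uses absolute cut-offs of 10% and 20% for its CVD risk groups, so predicted and observed risk should refer to the same horizon.

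**Working it through.** **The plan's own figures.** The sample size uses a 10-year ESRD incidence of 3.8%, taken as twice the 5-year 1.9%.

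- Development: 16 predictors × 50 events / 0.038 = 21,053, as stated.
- Validation: 14,307 × 0.038 = 543.7, that is, the stated 544 events. With AUC 0.7, 544 events and 13,763 non-events, the Hanley-McNeil standard error is 0.01275, and the 95% interval has total width 2 × 1.96 × 0.01275 = 0.050. This matches the stated precision if that means full width.
- Total: 21,053 + 14,307 = 35,360 per sex, as stated.

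These figures already rest on the 10-year incidence, so aligning the horizon does not change them.

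**Window length.** 1 July 2006 to 31 December 2016 is 3,837 days inclusive; 3,837 / 365.25 = 10.5 years, 5% longer than the horizon.

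**Size if every event in the window is counted.** Under a constant hazard with no competing deaths, F(10.5) = 1 − (1 − F(10))^1.05. Only the 3.8% comes from the plan; the other risks are assumed.

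| 10-year risk | Counted to 10.5 years | Relative excess |
|---|---|---|
| 3.8% (ESRD) | 3.99% | +4.9% |
| 10% | 10.47% | +4.7% |
| 20% | 20.89% | +4.4% |
| 30% | 31.24% | +4.1% |

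With Weibull hazards of shape 0.8 to 1.5 (assumed) and 10-year risks from 3.8% to 40%, the excess is about +3% to +7%.

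**In events.** In 14,307 validation subjects the excess is 14,307 × (0.03986 − 0.038) ≈ 27 events at 3.8%. Against the binomial standard error √(p(1 − p)/N), z is about 1.2. At an assumed 20% it is about 127 events, z about 2.7.

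**Methods read at 10 years.** In a simulation of 200,000 subjects with a true 10-year risk of 20%, the proportion with an event by year 10 was 20.0% (the Kaplan-Meier value when nobody is lost earlier). The crude proportion by 10.5 years was 20.9%. Later events do not affect an estimate read at 10 years.

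**Competing deaths.** For a non-fatal outcome with hazard a and other-cause death hazard b, both constant, the crude proportion with the event by time t is a/(a + b) × (1 − exp(−(a + b)t)). Take a 10-year risk of 10% from a model that censors deaths, and assume 10% other-cause mortality over 10 years. Then a = b = −ln(0.9)/10 = 0.01054:

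- Crude, to 10 years: 0.5 × (1 − exp(−0.2107)) = 9.50%.
- Crude, to 10.5 years: 0.5 × (1 − exp(−0.2213)) = 9.92%.

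The extra half-year still adds 9.92/9.50 − 1 = 4.5% to the count, but 9.92% lies below the predicted 10%. With 5% other-cause mortality the crude 10.5-year figure is 10.20%, above the prediction; with 20% it is 9.36%, well below.

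**The case against.** The strongest reply is that the plan separates a capture period from an estimation horizon. d)(iii) says when events are recorded; d)(iv) says incidence is reported over 10 years and adds a 10-year Kaplan-Meier estimate. A record longer than the horizon is ordinary in time-to-event work. The risk equation is set for 10 years through the survivor function, and the calibration test can be evaluated at 10 years. AUC depends on ranks and should hardly move.

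Most of this stands. It clears the Kaplan-Meier incidence and the model itself. It also rules out two stronger readings that a reader might infer. One is that the reported 10-year incidence is overstated: the documents support this only for a descriptive count that follows the d)(iii) window, and d)(iv) points to 10 years. The other is that a well-calibrated model must appear to under-predict: with crude event status, deaths from other causes pull the other way, and the documents give no mortality figure to settle the net sign. That sign is secure only for all-cause mortality.

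The reply does not cover the rest. d)(iii) defines how incidence is counted, not merely which records are extracted. The descriptive count is a separate analysis from Kaplan-Meier. The threshold, sensitivity and specificity, Brier score and calibration plot are set against observed events or incidence with no time attached. That some methods can be read at 10 years does not mean the plan requires it.

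**Conclusion.** The mismatch is real and its effect is modest and conditional. The plan counts events over 10.5 years, labels its results 10-year, and does not say where the two are brought together.

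If events after 30 June 2016 enter the exposed measures, their event count is higher than the correct 10-year count by about 4% to 5% relative. This assumes a constant hazard and no competing deaths; assumed Weibull shapes widen it to about 3% to 7%. The excess over the correct count is always upward. The direction of apparent miscalibration against the model is not fixed, because it also depends on how deaths are handled. No material shift in the ROC threshold has been shown. The sample size is not affected.

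The point should be corrected before analysis because it changes a stated counting rule and the correction costs almost nothing.

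**What to change.** State one horizon of 10 years for all reported incidence and validation measures, by either route:

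1. Censor every outcome administratively at 30 June 2016. Under a constant hazard without competing deaths, roughly 4% to 5% of the events in the window are then not used (for ESRD, (3.99 − 3.80)/3.99 ≈ 5%).
2. Keep all data to 31 December 2016 for fitting the Cox models, and evaluate every observed risk, the threshold, sensitivity and specificity, the calibration test and plot, and the Brier score at 10 years. No event is lost to model fitting.

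The descriptive incidence should use the same cut-off. The plan should also say how deaths before 10 years enter the observed side of the validation of non-fatal outcomes, since that affects the direction of any apparent miscalibration. Neither route needs new data or a larger sample.

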Multiple imputation will be used to handle missing data. Multiple imputation aims at increasing the power of the analysis and producing more reliable and applicable models within clinical practice. It also takes subjects with incomplete data into account to avoid unnecessary biases. Each missing value will be imputed five times by the chained equation method, which was equivalent to attain a relative efficiency of 95%. For each of the five imputed datasets, the same analysis will be performed with the five sets of results combined based on Rubin's rules.

2. Misclassification bias from the use of administrative database

This study relies on doctor entries of clinical diagnosis on DM complications and co-morbidity indicated by pre-defined by ICPC-2 and ICD-9-CM codes, which may be subject to misclassification bias. We will cross-check the diagnosis and prescription relation, and compare diagnosis from hospital and primary care records for the same patient in order to assess the data quality.

[Word Count: 3698]

e) Timetable of Work

June – August, 2017:

- i. Recruitment, training of RA
- ii. Meeting and discussion with HA co-investigators and Statistics team to confirm the data extraction schema and operation definitions

September – December, 2017

- i. Extraction of data from HA CMS
- ii. Update literature review

January – March, 2018:

- i. Data cleaning
- ii. Data analysis on the incidence & risk factors of DM complications and mortality

April – December, 2018:

- i. Data analysis to develop 6 prediction models
- ii. Validation of the prediction models

January -May 2019:

- i. Development of 10-year CVD risk prediction nomograms
- ii. Development of 10-year CVD risk prediction charts
- iii. Preparation of manuscripts for publications
- iv. Preparation of final report.

f) Existing Facilities:

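### The ESRD outcome accepts an eGFR below 15 with no requirement that it persist, so one temporary low reading can be recorded as a permanent event

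*Combined protocol and SAP*

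**What the plan says.** Section d)(iii) Methods, Definition of indicator DM complications, item 5, reads: "ESRD is defined by any of ICD-9-CM 250.3x, 585.x, 586.x, or an eGFR<15mL/min/1.73m²". The laboratory limb stands alone: meeting it is enough, without a code.

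The window is set at the start of the same section: "Each patient will be followed from 1 July 2006 to 31 December 2016". Events are dated as follows: "The incidence is counted from the earliest date of documented diagnosis defined by the relevant ICPC-2 and/ or ICD-9-CM coding". That rule mentions codes only, so an event that rests on eGFR alone has no stated date.

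Under Data collection, the data are to be "extracted by the HA statistics team from the HA clinical management system (CMS) database". The text does not say which eGFR tests are taken.

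Section d)(iv) puts the outcomes into Kaplan-Meier curves and then models: "Cox proportional hazard regressions with forward stepwise method will be used to develop the risk prediction models". Neither analysis has a recovery state.

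Under Strategies against anticipated problems, item 2, the safeguard against misclassification is: "We will cross-check the diagnosis and prescription relation, and compare diagnosis from hospital and primary care records for the same patient".

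ESRD also sets the size of the study: "The required sample size is based on the requirements for the development and validation of the least common DM complication of ESRD".

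**The concern.** ESRD is a lasting state, whereas eGFR can fall below 15 for a short time and recover. A definition met by a low value without any persistence condition does not separate the two. Once met, the event is final: the patient leaves the risk set as an ESRD case.

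Three things are at stake, all within the ESRD outcome. Objective 1 (incidence) would be biased upwards. Objective 2 (predictors) and objective 3 (the model) would rest on a mixture of lasting kidney failure and transient falls, which may have different predictors. Because ESRD is the rarest outcome, a given number of false events weighs most here.

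The planned validation would not show the problem. The validation sample is a random third of the same cohort, scored against events defined in the same way. Discrimination and calibration could both look satisfactory against a contaminated endpoint.

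**Working it through.** **1. Is there a persistence rule anywhere?** Item 5 gives a threshold and nothing else. The dating rule adds no condition on laboratory values. The misclassification check deals with diagnosis codes, prescriptions and agreement between sets of records. Appendix A is cited for operational definitions of risk factors, not of outcomes. No passage supplies a persistence rule.

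**2. The plan's own ESRD figures.** All are in section d)(ii), Sample size calculation.
- Incidence: 1.9% at 5 years, doubled to 3.8% at 10 years.
- Development: 16 predictors × 50 events ÷ 0.038 = 21,053, as stated.
- Validation: with AUC 0.7, 544 events and 13,763 non-events, the Hanley-McNeil standard error is 0.01275, so the full 95% interval width is 2 × 1.96 × 0.01275 = 0.050. Solving for the sample size gives 14,297 against the stated 14,307. This reads the precision of 0.05 as full width; read as half-width, 3,575 would be enough.
- Sum: 21,053 + 14,307 = 35,360 per sex.

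The figures reproduce. They serve here only as a base for scale.

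**3. Scale if 3.8% is the true incidence.** Let t be the share of patients without true ESRD who have one transient reading below 15 within 10 years. The documents do not give t; the values below are assumptions.

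False events = t × (1 − 0.038). Recorded incidence = 3.8% + false events. False share = false events ÷ recorded incidence. The last column is 21,053 × false events, beside 800 true events (21,053 × 0.038).

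| t | False events | Recorded incidence | False share | False events in 21,053 |
|---|---|---|---|---|
| 0.5% | 0.481% | 4.28% | 11% | 101 |
| 1% | 0.962% | 4.76% | 20% | 203 |
| 2% | 1.924% | 5.72% | 34% | 405 |

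**4. Scale if 3.8% already includes transient readings.** Let f be the share of counted events that a confirmation rule would remove (again an assumption). Incidence = 3.8% × (1 − f). Required size per sex = 800 ÷ incidence, plus the Hanley-McNeil validation size for an interval width of 0.05.

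| f | Incidence | Development + validation | Required per sex | Events per predictor in 21,053 | AUC interval width in 14,307 |
|---|---|---|---|---|---|
| 5% | 3.61% | 22,161 + 15,033 | 37,194 | 47.5 | 0.051 |
| 10% | 3.42% | 23,392 + 15,850 | 39,242 | 45 | 0.053 |
| 20% | 3.04% | 26,316 + 17,791 | 44,107 | 40 | 0.056 |
| 30% | 2.66% | 30,076 + 20,288 | 50,364 | 35 | 0.060 |

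The plan cites 120,857 patients from an earlier data set. With equal sexes that is about 60,428 each, and the planned 2:1 split gives about 20,143 per sex for validation. That covers the requirement at f = 20% and falls just short of the 20,288 needed at f = 30%. The count belongs to 1 January 2009 and may not reflect this study's exclusions, so it is only a guide.

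Steps 3 and 4 start from opposite premises and must not be added together.

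**The case against.** The text does not use the word single; it leaves persistence unstated, and the team may intend something stricter. That is fair as to intent. But item 5 is an operative rule, and an analyst who applies it as written will count one reading.

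A reader might infer that values taken during hospital admissions are known to be counted. The documents do not show this. The misclassification paragraph shows that hospital diagnoses are available for comparison; it says nothing on inpatient laboratory tests. What stands is that no setting is excluded.

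A reader might also infer that the ESRD model will in fact predict acute illness, through frailty or heart disease. The documents do not support that. Frailty is not a listed candidate predictor, and exclusion criterion 1 removes patients with coded CHD or heart failure at baseline. Age and other co-morbidity are candidates, but nothing shows how they relate to transient falls.

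The assumed rates are not evidence about this cohort, and 3.8% cannot be called the true rate: it is doubled from a previous study whose ESRD definition is not given. Both points are accepted, which is why both directions are shown.

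Finally, ESRD is not the main aim. Total CVD and all-cause mortality are, and the nomograms and charts cover only those. This limits the weight of the point but does not remove it, since ESRD falls under objectives 1 to 3 and drives the sample size.

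**Conclusion.** The concern holds in a limited form. The laboratory limb has no persistence requirement, no check in the plan would catch a temporary value, and the analyses make any such event permanent. The effect is confined to ESRD incidence, predictors and model.

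Its size cannot be found in the documents and may be small. If true incidence is 3.8% and transient readings occur in 0.5% to 2% of patients without ESRD, between about 11% and 34% of recorded events would be false. If 3.8% already contains transient readings, true incidence is below 3.8% and the stated sample size is somewhat optimistic for a confirmed endpoint.

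A reader might conclude that the stated sample size is wrong. It is not shown to be: it follows from its stated inputs. A correction is worthwhile because it is cheap and the sensitivity analysis would measure the unknown share directly.

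**What to change.** For the laboratory limb of the outcome definition, require eGFR below 15 on two readings at least 90 days apart, with no reading of 15 or above between them. Leave the code limb unchanged.

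Date an eGFR-only event at the confirming reading, and extend the dating rule, which now covers codes only, to say so. Dating it at the first low reading would make an event on that day depend on the patient surviving and being tested at least 90 days later.

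Report the single-reading definition as a sensitivity analysis, with incidence and model coefficients side by side.

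The cost is one rule applied to the eGFR dates and values that the present definition already needs, plus one repeat analysis. The downside is that true cases who die or leave before a second reading are missed unless coded, as are patients whose first low reading falls too late for confirmation by 31 December 2016 (after 2 October 2016, counting back 90 days). The ESRD event count will fall somewhat, so events per predictor should be checked again once the confirmed count is known.
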